5.2. Efficacy Analyses

5.2.1. Best Overall Response

The frequency (number and percentage) of patients with BOR of CR, PR, SD, PD, non CR/non PD, and NE (not evaluable) will be provided along with a summary of the objective response rate (ORR) and the corresponding exact 95% 2-sided confidence interval using standard methods based on the binomial distribution, by hepatic function group. ORR is defined as the percent of patients with complete response (CR) or partial response (PR), that is subsequently confirmed, based on investigator evaluation, according to RECIST v1.1 (Appendix 1), relative to the response-evaluable population. Confirmed responses are those that persist on repeat imaging study at least 4 weeks after the initial documentation of response. Designation of best response of SD requires the criteria to be met at least once after the first dose of medication, at a minimum interval of 6 weeks. Since efficacy is a secondary objective in this study, tumor response derivation will not be performed programmatically and the investigator overall tumor assessment (IOTA) of best response will be used.

5.2.2. Duration of Response

Duration of response (DR) is defined as the time (in weeks) from the first documentation of objective tumor response (CR or PR) that is subsequently confirmed, to the first documentation of objective tumor progression or death on study due to any cause, whichever occurs first. If tumor progression data include more than 1 date, the first date will be used. DR (in weeks) will be calculated as (first date of PD or death - first date of CR or PR +1)/7.02. DR will be calculated based on RE population for the subgroup of patients with a confirmed objective tumor response. The censoring rules for DR are presented as below.

Patients with inadequate baseline disease assessment are censored at the start date.

In this study antitumor activity will be assessed through radiological tumor assessments conducted at screening and every odd-numbered cyles (6 weeks) until disease progression. while on treatment and whenever disease progression is suspected (eg, symptomatic deterioration). The allowable time window for disease assessments is ± 1 week. Therefore time without adequate assessment is defined as 14 weeks (12 weeks +2 weeks). Patients lacking an evaluation of tumor response after treatment start or for whom the first on-study disease assessment occurs after Week 14 and shows progression, will also have their event time censored on the date of treatment start unless death occurs within (and including) Week 14 (in which case the death is an event).

If patients have at least 1 on-study disease assessment, PFS data will be censored on the date of the last evaluable on-study tumor assessment documenting absence of progressive disease for patients:

- Who are alive, on study, have not started anti-tumor treatment other than study medication and progression free at the time of the analysis;
- Who are given anti-tumor treatment other than the study medication and prior to documented disease progression or death on study. In this case, the last evaluable assessment prior to start of the anti-tumor treatment will be used.

For patients who have at least 1 on-study disease assessment and who have documentation of disease progression or death on study after ≥ 2 , consecutive missed tumor assessments (ie, >14 weeks after last on-study tumor assessment), the date of censoring will be the last assessment documenting no progression prior to the missed assessments.

DR will be summarized by hepatic function group using the Kaplan-Meier method.³ The median event time (if appropriate) and 2-sided 95% CI for the median⁴ will be provided. Since the number of patients in each hepatic function group is small, and number of CR or PR would be even smaller, the use of Kaplan-Meier method may be limited and the DR will be also summarized using descriptive statistics.

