Serious and non-serious adverse event monitoring 	Х	$\rightarrow$	$\rightarrow$	$\rightarrow$	$\rightarrow$		$\rightarrow$	$\rightarrow$	Х
Concomitant treatment(s) 	Х	$\rightarrow$	$\rightarrow$	$\rightarrow$	$\rightarrow$		$\rightarrow$	$\rightarrow$	Х
Suicidal Ideation and Behavior 		Х			Х		X (up to Cycle 6 and then Day 1 of every other cycle)	Х	
Other assessments									
Pharmacokinetics 		Х	Х	Х	Х				
CCI									

Abbreviations:  $\rightarrow$  = ongoing/continuous event; CT = computed tomography; ECG = electrocardiogram; ECOG = Eastern Cooperative Oncology Group; ECHO = echocardiogram; HBV = hepatitis B virus; HCV = hepatitis C virus; LVEF = left ventricular ejection fraction; MRI = magnetic resonance imaging; MUGA = multigated acquisition scan; RECIST= Response Evaluation Criteria for Solid Tumors. (X) – to be completed if not performed within 7 days of the first dose of lorlatinib.

- a. Day relative to start of study treatment (Day 1).
- 1. Screening: To be obtained within 28 days prior to the start of study treatment.
- 2. Study Treatment: All assessments should be performed prior to dosing with lorlatinib unless otherwise indicated. Acceptable time windows for performing each assessment are described in the column headers. All cycles are 21 days in duration. Following completion of Cycle 2, ongoing patients on lorlatinib will need to visit the clinic on Day 1 of every cycle for assessments. Enough study medication for one cycle of treatment will be dispensed at each clinic visit. Some assessments such as Liver Function Assessment and physical examination could be performed more frequently at the discretion of investigator according to the standard practice at the site. Tumor assessments may occur at every odd-numbered cycle or according to standard practice for the indication at the site.
- 3. Cycle 1/Day 1: Blood chemistry, hematology, coagulation, lipids, and physical examination not required if acceptable corresponding screening assessment was performed within 7 days prior to the start of study treatment. Values closest prior to the first dose of lorlatinib will be used for baseline.
- 4. Informed Consent: Must be obtained prior to undergoing any study-specific procedures.

- 5. Medical/Oncological History: To also include information on prior medications, smoking history, prior treatment regimens. Will be updated on Cycle 1 Day 1 before the start of treatment.

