# 9.5. Efficacy Analysis

# 9.5.1. Antitumor Activity Analysis

The response-evaluable population is defined as all patients in the safety analysis population who have an adequate baseline tumor assessment. The response-evaluable population will be the primary population for evaluating clinical antitumor activity data.

Objective Response Rate (ORR) is defined as the percent of patients with complete response (CR) or partial response (PR) based on investigator evaluation, according to RECIST v1.1 (Appendix 6), relative to the response-evaluable population. Designation of best response of stable disease (SD) requires the criteria to be met at least once after the first dose of medication, at a minimum interval of 6 weeks.

Duration of response (DR) will be measured from the date that an objective tumor response (CR or PR) is first documented (whichever occurs first) to date of objective tumor progression or death due to any cause, whichever occurs first.

Descriptive statistics will be used to summarize baseline characteristics, treatment administration, and antitumor activity endpoints overall and, if applicable, separated by treatment group (as defined by hepatic function and starting dose level) and/or tumor type, as applicable. Data will also be displayed graphically, where appropriate. The ORR will be summarized along with the exact 2-sided 95% confidence interval using the exact method based on the F-distribution. DR will be summarized using Kaplan-Meier method, where appropriate.

Patients who have prior major gastrointestinal surgery removing part of the gastrointestinal tract and/or gall bladder will be excluded from descriptive summary and statistical analysis for efficacy endpoints, but will be listed for their tumor assessment.

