5.4.3. Study Treatment Exposure

Drug administration of PF-06463922 will be described on the Safety Analysis set in terms of:

- Duration of Treatment in months (Last Treatment Date C1D1 date + 1)/30.44.
- Days on drug in months (duration of treatment in days- days of interruption)/30.44.
- Overall relative dose of PF-06463922. Details for calculation of relative dose are provided in Appendix 1.

The mean, median and range will be provided for these variables by hepatic function group.

Number and percentage of patients having dose reductions /interruptions will be provided by hepatic function group. An interruption is defined as a 0 mg dose administered for more than 1 day.

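### SAP 5.2.2 converts duration of response from days to weeks with 7.02 instead of 7, understating each unrounded value by 0.285%

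*SAP*

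**What the plan says.** SAP 5.2.2 sets the unit in its first sentence: "Duration of response (DR) is defined as the time (in weeks) from the first documentation of objective tumor response (CR or PR" onward, ending at objective progression or death. It then gives the derivation: "first date of PD or death - first date of CR or PR +1)/7.02". The numerator counts days, including both the first and the last.

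The same section describes the imaging schedule as "every odd-numbered cyles (6 weeks) until disease progression". The protocol's Schedule of Activities fixes the cycle length: "All cycles are 21 days in duration".

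Protocol 9.5.1 defines the endpoint without a unit or a divisor: "Duration of response (DR) will be measured from the date that an objective tumor response (CR or PR) is first documented", running to progression or death. It therefore neither supports nor overrides 7.02. On reporting, SAP 5.2.2 states: "DR will be summarized by hepatic function group using the Kaplan-Meier method". A median with a 95% interval is to be given if appropriate, and descriptive statistics are given as well.

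**The concern.** A day count divided by 7.02 is not a number of weeks. DR is a named secondary endpoint in both documents, and this line is its operative derivation rule, so a programmer who follows the SAP will code the wrong constant. Section 5.2.2 also ends up with two week lengths: 7 days for the imaging schedule and 7.02 for the endpoint measured on that schedule.

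What is at stake is the accuracy of the figures in weeks. Responders will be few, so individual durations are likely to be visible in the report. A reader who converts the dates in the ordinary way would get slightly different unrounded values.

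**Working it through.** **Inputs**

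- Divisor: 7.02 (SAP 5.2.2).
- Numerator: D = end date − start date + 1, in days (SAP 5.2.2).
- Cycle length: 21 days (protocol, Schedule of Activities).
- Imaging interval: every second cycle, stated as 6 weeks (SAP 5.2.2).
- Month divisor used elsewhere: "Days on drug in months (duration of treatment in days- days of interruption)/30.44" (SAP 5.4.3).

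**Step 1. Can 7.02 be reproduced as days per week?**

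From the documents' own schedule: 2 × 21 / 6 = 42 / 6 = 7.00. It is not reproduced.

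Two other routes round to 7.02: 365.25 / 52 = 7.024 and 30.44 × 12 / 52 = 7.025. Both treat a year as exactly 52 weeks. Either could be the origin, but that is an assumption, since the SAP does not say. An average divisor is legitimate for months, whose length varies. Weeks do not vary.

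**Step 2. Size of the error**

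Reported / correct = (D / 7.02) / (D / 7) = 7 / 7.02 = 0.99715, a shortfall of 0.285%. The correction factor is 7.02 / 7 = 1.00286.

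| D (days) | D / 7.02 (weeks) | D / 7 (weeks) | Shortfall (days) | At one decimal |
|---|---|---|---|---|
| 42 | 5.983 | 6.000 | 0.12 | 6.0 and 6.0 |
| 84 | 11.966 | 12.000 | 0.24 | 12.0 and 12.0 |
| 98 | 13.960 | 14.000 | 0.28 | 14.0 and 14.0 |
| 245 | 34.900 | 35.000 | 0.70 | 34.9 and 35.0 |
| 365 | 51.994 | 52.143 | 1.04 | 52.0 and 52.1 |

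The shortfall reaches one full day at D = 1 / (1 − 7/7.02) = 351 days.

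**Step 3. Rounding**

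Over D = 1 to 730 days, 122 values print identically at one decimal, the largest being 225 days. Below 60 days only seven differ: 20, 27, 34, 41, 48, 53 and 55.

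**Step 4. The inclusive count**

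Against plain elapsed days d = D − 1, the two effects cancel when (d + 1) / 7.02 = d / 7, that is 7d + 7 = 7.02d, so d = 350. Up to 349 elapsed days the +1 outweighs the divisor. The shortfall is therefore relative to the SAP's own inclusive count.

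**Step 5. Effect on the analysis**

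A common multiplier leaves the ordering of durations, the risk sets and the event indicators as they were. The Kaplan-Meier curve keeps its shape on a time axis compressed by 0.285%, and the median and its limits shrink by the same factor.

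The 14-week missed-assessment rule would not move even if it were coded with the same divisor: 14 × 7 = 98 and 14 × 7.02 = 98.28, and a gap in whole days first exceeds both at 99.

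**The case against.** The strongest reply is that this does not matter. Progression is read from scans every 6 weeks with a window of ±1 week, so uncertainty in dating the event is far larger than a fraction of a day. SAP 4.1 plans no formal hypothesis testing, and the primary endpoints are steady-state AUC24 and Cmax. SAP 5.2.2 itself expects very few responses and doubts that Kaplan-Meier will be of much use, so there may be no median to distort. The censoring text in the same section refers to PFS, which is not a listed endpoint, and that deserves attention first. All of this stands, and it limits the point to a minor one. It does not make 7.02 correct.

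A reader might also infer three stronger things that the documents do not support:

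- **That the durations cannot be reproduced from the dates.** They can: the SAP gives the whole formula, and applying it returns the reported value. The fault is a mis-scaled unit.
- **That every printed duration will be too short.** This holds before rounding and relative to the inclusive count. Neither document fixes the number of decimals for DR, and at one decimal many values agree.
- **That the analysis is biased in a way that could alter a finding.** A constant rescaling changes no event status, no ordering and no conclusion.

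Could 7.02 be 7.0 followed by a reference mark 2? That is unlikely. Reference marks elsewhere in the SAP appear as superscripts, and reference 2 concerns binomial confidence limits.

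**Conclusion.** The divisor is wrong as written, and the consequence is minor. Unrounded DR values, and any median, confidence limit or descriptive statistic in weeks, are understated by 0.285%: about 0.12 day at 6 weeks and 1.04 days at 365 days.

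This rests on two assumptions. The first is that the SAP's inclusive day count is the intended numerator. The second is that censored durations are converted with the same divisor: the printed formula names only progression or death as the end date, and no separate conversion is given for censored cases. No expected duration is stated in either document, so the durations in the table are illustrations, not predictions.

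**What to change.** Replace 7.02 with 7 in the DR formula in SAP 5.2.2 and in the analysis program, and apply the same divisor to censored durations. The cost is one constant in the text and one in the code. It needs no new data, leaves the clinical definition of the endpoint as it is, and does not affect the protocol's definition, which contains no divisor.

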5.3. Subset Analyses

None

5.4. Baseline and Other Summaries and Analyses

5.4.1. Baseline Summaries

Summaries of baseline variables, patient and disease characteristics and prior anti-cancer treatments will be provided on the safety analysis set. The summaries will be presented overall, by hepatic group and by tumor type (as appropriate). All data collected as part of screening will be listed.

The following demographic and baseline characteristics will be summarized by number and percentage:

- Gender(male, female).
- Age (<18, 18-44; 45-64, ≥65).
- Race (white, black, asian, other).
- Eastern Cooperative Oncology Group (ECOG) Performance status.

Age (continuous), height (cm), weight (kg), Body Mass Index (BMI) (kg/m²), will be summarized with descriptive statistics (mean, standard deviation, minimum, and maximum).

BMI (kg/m²) is computed as weight (kg) /(height (cm)*0.01)**2

Patient characteristics at study entry such as diagnosis, and medical history will be summarized in frequency tables, and descriptive statistics will be provided for quantitative variables.

The number and percentage of patients in each of the following prior anti-cancer therapy categories will be tabulated:

- Patients with at least one prior non-drug treatment/surgeries;
- Patients with at least one prior radiotherapy;
- Patients with at least one prior systemic therapy.

5.4.2. Study Conduct and Subject Disposition

Subject evaluation groups will show end of study subject disposition and will show which subjects were analyzed for pharmacokinetics, efficacy, as well as for safety (adverse events and laboratory data). Frequency counts (numbers and percentages) will be supplied for subject discontinuation(s) by hepatic function group.

5.4.2.1. Patient Disposition

Discontinuation from study will be summarized using full analysis set. Discontinuation from study treatment will be summarized using safety analysis set. Patients not completing the study will be listed along with the reason for their discontinuation.

Discontinuations from study treatment due to adverse events will be identified as either related or not related to study treatment. If causality is missing the event will be considered related to treatment. If multiple events lead to study treatment discontinuation and at least one was considered related, discontinuation will be reported as related to study treatment.

Subject discontinuations, temporary discontinuations or dose reductions due to adverse events will be detailed and summarized by hepatic function group.

5.4.2.2. Protocol Deviations

Subjects who experience events that may affect their PK profile (eg., lack of compliance with dosing) may be excluded from the PK analysis. At the discretion of the pharmacokineticist a concentration value may also be excluded if the deviation in sampling time is of sufficient concern or if the concentration is anomalous for any other reason.

A full list of protocol deviations will be compiled and reviewed to identify major and minor deviations prior to database closure.

5.4.3. Study Treatment Exposure

Drug administration of PF-06463922 will be described on the Safety Analysis set in terms of:

- Duration of Treatment in months (Last Treatment Date C1D1 date + 1)/30.44.
- Days on drug in months (duration of treatment in days- days of interruption)/30.44.
- Overall relative dose of PF-06463922. Details for calculation of relative dose are provided in Appendix 1.

The mean, median and range will be provided for these variables by hepatic function group.

Number and percentage of patients having dose reductions /interruptions will be provided by hepatic function group. An interruption is defined as a 0 mg dose administered for more than 1 day.

5.4.4. Concomitant Medications and Non-Drug Treatments

All concomitant medication(s) as well as non-drug treatment(s) will be provided in the listings.

5.4.5. Columbia Suicide Severity Rating Scale (C- SSRS)

Individual patient data will be presented in patient data listings.

5.5. Safety Summaries and Analyses

Summaries and analyses of safety parameters will be provided based on the on-treatment period unless otherwise specified, by hepatic function group for the Safety Analysis Set. For all safety analyses, only descriptive methods will be used without any formal statistical testing.

The on-treatment period is defined as the time from the first dose of study treatment through and including 28 days after last dose or start of new anti-cancer drug therapy, whichever occurs first [minimum (28 days + last dose of study treatment, start day of new anti-cancer drug therapy - 1 day)]. Adverse events occurring on the same day as the first dose of study treatment will be considered to have occurred during the on-treatment period. All other safety assessments which occur on the same day as the first dose of study treatment will be considered baseline assessments.

Safety data collected outside the on-treatment period as described above will be listed but not summarized.

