- Groups A1 and A2 (Normal): patients with normal liver function will be included in this study as matching control patients (Group A1 for Group B and Group A2 for Group C). If the dose for moderate hepatic impairment group (Group C) is selected to be the recommended clinical dose of 100 mg QD, the control group A2 will not be needed to be enrolled. There will be no control group designated to match severe group. However, if a decision has been made to use the same dose for severe and moderate patients, the half of the control Group A2 will be matching Group C and half will be matching Group D.

Child-Pugh scores (criteria listed in Appendix 3) will be calculated and recorded as part of the liver function testing prior to the start of the first lorlatinib dose, but will not be used to stratify patients into treatment groups.

The enrollment of approximately 76 advanced cancer patients is anticipated in this study in order to have 8 PK-evaluable patients in each of Groups A1, A2, B and C, and 6 PK-evaluable patients in Group D for final statistical analysis. Evaluable patients are those who complete the planned PK sample collection on Cycle 2 Day 1 and have no lorlatinib dose modification until completion of Cycle 2 Day 1 PK evaluation. Patients who are not evaluable for PK will be replaced.

Each patient will be treated with repeated oral once daily doses of lorlatinib in 21-day cycles until disease progression, patient refusal, or unacceptable toxicity occurs.

The planned dosing schedule for each treatment group is as follows (Table 4):

	Group B	Group C	Group D	Group A1	Group A2
Hepatic Function	Mild	Moderate	Severe	Normal	Normal
Starting Lorlatinib Dose	100 mg QD	50 mg QD or otherwise determined in the first stage	determined based on preliminary safety and PK data	100 mg QD	the same dose as Group C at the second stage
Lorlatinib Dose After PK Assessment	100 mg QD	50 mg QD or otherwise determined in the first stage	determined based on preliminary safety and PK data	100 mg QD	100 mg QD

Table 4.Lorlatinib Dosing Schedule

The dose schedule may be modified as necessary for individual patients according to tolerability (see Table 6 for detailed dose modification strategy).

For Group C, a two-stage enrollment will be applied.

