• In the first stage, 3 PK-evaluable patients will be enrolled to receive the starting dose of 50 mg QD lorlatinib. On completion of PK sample collection through Cycle 2 Day 1 from these 3 patients, PK analysis will be performed. Upon review of the PK and tolerability of these 3 patients, a decision on dose schedule for remaining patients in the second stage will be made.

- In the second stage:
  - If it is decided to keep the planned dosing schedule (50 mg QD) for patients in Group C with moderately impaired liver function, 5 additional patients will be enrolled to have a total of 8 PK evaluable patients.
  - If a different dosing schedule is proposed for the remaining patients in Group C based on safety and PK in the first 3 subjects, then more patients will be enrolled to this group to have 8 PK evaluable patients and receive the proposed dosing schedule. The control patients in Group A2 should receive the same lorlatinib dose as proposed for the second stage in Group C until completion of PK assessment on Cycle 2 Day 1 and then switch to 100 mg QD beyond Cycle 2 Day 1. At the new dose level, the first 3 patients should be dosed one at a time with at least one week apart until some safety information at this dose level is obtained.

The enrollment for patients with severe hepatic impairment (Group D) will only be started when the dose for patients in the second stage of Group C has been determined and has been tolerated in at least one patient. The initial lorlatinib dose for Group D might be the same as the second stage Group C dose or otherwise determined by sponsor based on available preliminary safety and PK data at that time. The dosing regimen for Group D will be communicated to sites. Patients in Group D will not be matched by any control group. Initially (the first 3 patients), the patient should be dose one by one with at least 1 week apart until some safety information is obtained at the dose level.

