# **Adverse Events**

Adverse Events (AEs) will be coded by system organ class (SOC) and preferred term according to Medical Dictionary for Regulatory Activities (MedDRA) terminology. AE severity will be graded according to NCI Common Terminology Criteria for Adverse Events (CTCAE) version 4.0.3.

A listing of all AEs including detailed information collected for each AE (description of event, onset date/time, duration, seriousness, severity, relationship to study drug, action taken, clinical outcome) will be presented.

The number and percentage of patients who experienced any: AE, serious AE (SAE), treatment related AE, and treatment related SAE will be summarized. Emphasis in the analyses will be placed on AEs classified as treatment emergent. The analyses will summarize AEs both on the entire study period and by cycle (Cycle 1 and Cycles beyond 1).

Additional summaries of adverse events (AE) and of other safety data will be presented in tabular and/or graphical format and summarized descriptively, as appropriate.

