2.1. Study Objectives

Primary:

• To evaluate the effect of hepatic impairment on the steady state pharmacokinetics of lorlatinib.

Secondary:

- To evaluate the effect of hepatic impairment on the safety of lorlatinib in advanced cancer patients.
- To evaluate the antitumor activity of lorlatinib in advanced cancer patients.

CCI

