Patients in Groups A1 (Normal hepatic function) and B (Mild hepatic impairment) will receive a starting lorlatinib dose of 100 mg (4×25 -mg tablets) QD. The first 3 patients in in Group C (Moderate hepatic impairment) will receive a starting lorlatinib dose of 50 mg (2×25 -mg tablets) QD. Patients in control Group A2 (Normal hepatic function) will receive the same starting lorlatinib dose as stage 2 of Group C, which could be 50 mg (2×25 -mg tablets) QD or as otherwise determined during the second stage of Group C, and switch to 100 mg (4×25 -mg tablets) QD after completion of PK assessment on Cycle 2 Day 1.

Enrollment into control Group A2 will only be started after the first stage for Group C has been completed and a decision on dose schedule for the stage 2 subjects in Group C has been made. Patients in control group should match patients in the respective hepatic impaired group by the following criteria:

- The mean body weight in control group will be within ±20 kg of the mean body weight of the patients in respective hepatic impaired group.
- The mean age in control group will be within ± 10 years the mean age of the patients in respective hepatic impaired group.
- The gender ratio in control group will be similar (±2 patients per gender) to those in respective hepatic impaired group.

Once all the patients complete their planned PK collection, data collection for the primary objective of the study will be accomplished. After data collection for the primary objective has been completed, the sponsor could generate a study report including all PK data and other data, as defined in the Sponsor-maintained statistical analysis plan. In this case, a supplement study reported will then be generated when all patients completed the study.

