5. ANALYSES AND SUMMARIES

All summaries will be provided by hepatic function group. Patients treated on different dose levels within the same hepatic function group will be categorized by dose level (eg, Group C split into Group C1 and C2).

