5.5.2. Laboratory Data

Hematology, biochemistry, and lipid results will be programmatically graded according to the NCI CTCAE Version 4.03.

The number and percentage of patients who experienced laboratory test abnormalities will be summarized according to worst toxicity grade observed on treatment for each lab assay. Worst case is defined as the maximum post-baseline CTCAE grade using scheduled and unscheduled visits. The analyses will summarize laboratory tests on the entire study period. Shift tables of baseline grade by maximum post-baseline CTCAE grade will also be presented.

Patients who developed Grade \geq 3 toxicity will be listed.

An evaluation of Drug-Induced Serious Hepatotoxicity (eDISH) plot will also be created, by graphically displaying post-baseline:

- peak serum ALT(/ULN) vs peak total bilirubin (/ULN) including reference lines at ALT=3×ULN and total bilirubin=2×ULN.
- peak serum AST(/ULN) vs peak total bilirubin (/ULN) including reference lines at AST=3×ULN and total bilirubin=2×ULN.

In addition, a listing of all TBILI, ALT, AST and ALP values for patients with a post-baseline TBILI $\ge 2 \times ULN$, ALT $\ge 3 \times ULN$ or AST $\ge 3 \times ULN$ will be provided.

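### If Group C is not dosed at 100 mg QD, control Group A2 changes dose after Cycle 2 Day 1, so the SAP's whole-period incidence, worst-grade and maximum-value safety tables mix liver function with dose for C versus A2

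*SAP*

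**What the plan says.** The safety aim is a secondary objective (SAP 2.1): "To evaluate the effect of hepatic impairment on the safety of lorlatinib in advanced cancer patients". Group A2 is the control matched to Group C (Protocol 3.1, SAP 2.2).

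Dosing: A2 patients "will receive the same starting lorlatinib dose as stage 2 of Group C" (SAP 2.2). They keep that dose "until completion of PK assessment on Cycle 2 Day 1 and then switch to 100 mg QD beyond Cycle 2 Day 1" (Protocol 3.1). In the Protocol 3.1 dosing table, the Group C entry is the same for the starting dose and for the dose after PK assessment: "50 mg QD or otherwise determined in the first stage". If Group C's dose is set at 100 mg QD, A2 is not enrolled.

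Safety analysis: SAP 5.5 opens with "Summaries and analyses of safety parameters will be provided based on the on-treatment period unless otherwise specified, by hepatic function group". It ends the on-treatment period 28 days after the last dose, or at new anti-cancer drug therapy if that comes first. SAP 5 adds a general rule: "Patients treated on different dose levels within the same hepatic function group will be categorized by dose level". Its example is splitting Group C into C1 and C2.

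The protocol plans finer tables. On adverse events, Protocol 9.4 says: "The analyses will summarize AEs both on the entire study period and by cycle (Cycle 1 and Cycles beyond 1". It says the same of laboratory tests. Protocol 9.4.1 summarises ECG intervals by hepatic function and dose. In the SAP, 5.5.1 is silent on a cycle split. SAP 5.5.2 says: "The analyses will summarize laboratory tests on the entire study period". SAP 5.5.4 summarises ECG values by hepatic group and nominal visit, without naming dose.

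**The concern.** A2 exists so that Group C can be set against patients with normal liver function on the same dose. For PK this works, because the comparison is complete before A2 changes dose. For safety, the dose match ends at the switch, but the observation window runs on for as long as the patient is treated.

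The tables at risk are those that keep one value per patient from the whole period: whether an event ever occurred, its worst grade, or the largest value. In A2 that value may come from time at 100 mg; in Group C it comes from Group C's own dose. A difference between the two columns cannot then be credited to liver function. If toxicity rises with dose, the error runs in the unhelpful direction: extra toxicity from moderate impairment could be hidden, or impaired patients could seem to tolerate lorlatinib better than the controls.

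**Working it through.** The documents give no figure for this point, so there is none to reproduce. The check has three parts.

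**1. Which summaries are affected**

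- Mixed for C versus A2: adverse event incidence and worst grade (SAP 5.5.1), worst laboratory grade (5.5.2), maximum-change and extreme-value vital-sign categories (5.5.3), maximum PR and QTc categories (5.5.4), LVEF threshold categories (5.5.5), highest ECOG score (5.5.7).
- Dose-matched through Cycle 2 Day 1: by-visit descriptive statistics for vital signs (5.5.3) and ECG (5.5.4), including the serial ECGs on Cycle 2 Day 1.
- LVEF by visit: after baseline, the Schedule of Activities first plans it on treatment at Cycle 3 Day 1, which follows the switch. No scheduled on-treatment LVEF visit is dose-matched.

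The dose-level rule in SAP 5 sorts patients. It gives no rule for one patient who takes two planned doses in sequence. SAP Appendix 1 foresees a change of intended dose per protocol, but only when calculating relative dose, where it holds the intended dose fixed.

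**2. Size of the dose imbalance**

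Inputs: 21-day cycles, with the Cycle 2 Day 1 dose still at the matched level, give 21 + 1 = 22 matched doses. Group C is at 50 mg QD (the planned dose); A2 takes 100 mg afterwards. Durations d are assumed, with full compliance and no reductions.

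- Share of days at 100 mg = (d − 22)/d
- Mean daily A2 dose = (22 × 50 + (d − 22) × 100)/d
- Cumulative dose ratio A2/C = (22 × 50 + (d − 22) × 100)/(50d)

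| d (days) | Share at 100 mg | Mean daily A2 dose | Ratio A2/C |
|---|---|---|---|
| 22 | 0% | 50 mg | 1.00 |
| 42 | 20/42 = 48% | 3,100/42 = 73.8 mg | 3,100/2,100 = 1.48 |
| 84 | 62/84 = 74% | 7,300/84 = 86.9 mg | 7,300/4,200 = 1.74 |
| 126 | 104/126 = 83% | 11,500/126 = 91.3 mg | 11,500/6,300 = 1.83 |

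Over days 42 to 126 the ratio would run from 1.16 to 1.28 if Group C's dose were 75 mg, and from 2.43 to 3.48 if it were 25 mg.

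**3. What that could do to an incidence table**

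This is an illustration with no true liver effect. Assume a constant event hazard with 20% risk per 21 days at the starting dose, h = −ln(0.8)/21, and a hazard m times higher at 100 mg. At d = 84:

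- Group C: 1 − exp(−84h) = 59.0%.
- A2: 1 − exp(−h(22 + 62m)) = 70.5%, 78.8% and 89.0% for m = 1.5, 2 and 3.
- C minus A2: −11.5, −19.8 and −30.0 percentage points, all spurious. With m = 1 the difference is 0.
- Cycle 1 alone: 20% in both groups for every m.

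The values of m and the 20% are assumptions; the documents quantify no dose–toxicity relation.

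**The case against.** Several points can fairly be made against this.

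- **No safety contrast is specified.** Test and Reference pairs are defined only for PK, and safety is descriptive with no formal testing. So no error rate is affected. But the secondary objective asks about the effect of impairment on safety, and the side-by-side columns are how it will be read.
- **The SAP supplements the protocol.** SAP 2 says so, and the Cycle 1 adverse event table may therefore still be intended. A reader might infer that the SAP removed the adverse event split. Its silence does not show that, since SAP 2 also allows the SAP to modify the protocol. For laboratory tests the difference is explicit.
- **Much of SAP 5.5 is by visit.** A reader might infer that every safety summary is confounded. The by-visit ECG and vital-sign statistics through Cycle 2 Day 1 are not.
- **Duration is unknown.** A reader might infer that A2's tables will mostly reflect 100 mg. At 42 days the share is 48%, under half, and patients who stop before the switch contribute no mismatch. About 76 are to be enrolled for 38 PK-evaluable, so early loss may be common.
- **Time at a dose is not event bias.** This stands. Protocol 1.2.1.2.1.1 reports that CNS effects at higher doses led to re-testing of lower ones, which makes a dose relation plausible but gives no rate.

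These points narrow the concern. None supplies a rule for A2 data after the switch.

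**Conclusion.** The concern holds for the incidence, worst-grade, maximum-value and threshold tables, and only if Group C's dose is not 100 mg QD. In that case, following SAP 5.5 as written confounds the C versus A2 reading with dose. With Group C at 50 mg, A2's cumulative dose would be 1.48 to 1.83 times Group C's at assumed durations of 42 to 126 days. The effect on event rates cannot be sized from the documents. Its likely direction, if toxicity rises with dose, is to make moderate impairment look safer than it is relative to normal function.

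The primary PK comparison is untouched, because it is completed before the switch. Nor do the documents support reading this as a fault in the dosing plan: the gap lies in how the safety data are tabulated. It should be corrected because a secondary objective depends on these tables and the remedy is cheap.

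**What to change.** Amend SAP 5.5 and its subsections as follows.

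1. For the affected tables, present A2 in two columns: before, and from, the first 100 mg dose after Cycle 2 Day 1.
2. Compare the pre-switch A2 column with Group C cut at the same study day. Use this single cut, so that the Cycle 2 Day 1 assessments, including the serial ECGs, stay in the matched comparison.
3. Restore the Protocol 9.4 split (Cycle 1, later cycles) for adverse events and laboratory tests, and the Protocol 9.4.1 split by dose for ECG.
4. Label LVEF results by dose; a cut at the switch would leave no scheduled on-treatment LVEF visit to compare.
5. Keep the whole-period tables, labelled as not dose-matched for C versus A2.

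The cost is SAP wording and an extra set of tables. No new data and no dosing change are needed. The drawback is that the dose-matched safety comparison covers only about three weeks, so later-onset toxicity can be described but not compared at equal dose. That limit comes from the design.
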